#### **8.4. Emergency Unblinding of Treatment Assignment**

Not applicable.

## 8.5. Pregnancy

Pregnancy, in and of itself, is not regarded as an AE unless there is suspicion that study drug may have interfered with the effectiveness of a contraceptive medication or method. When a pregnancy has been confirmed, including the pregnancy of a male subject's female partner that occurs during the study, or within 120 days of completing the study or 30 days following cessation of treatment if the subject initiates new anticancer therapy, whichever is earlier, the following procedures should occur:

- The investigator must notify the sponsor or its designee immediately.
- The study drug must be discontinued immediately.
- The subject must be withdrawn from the study.
- The EOT visit evaluations must be performed.
- The investigator must complete and submit the Pregnancy Initial and Follow-Up Report forms to the sponsor or its designee.
- A serum pregnancy test must be performed to confirm the urine pregnancy test result. (The serum test should be performed at the investigative site to ensure the test will be performed promptly and the result available immediately for review.)

If a negative serum test does not confirm the urine pregnancy test result, then:

- The investigator will use his or her expert judgment, based on an assessment of the potential benefit/risk to the subject, to determine if it is in the subject's best interest to resume study drug and continue participation in the study.

**To ensure subject safety, each pregnancy in a subject during maternal or paternal exposures to study drug must be reported within 24 hours of learning of its occurrence.** Data on fetal outcome and breastfeeding are collected for regulatory reporting and drug safety evaluation. Follow-up to each pregnancy should be conducted, by following until the first well-baby visit. Pregnancy should be recorded on a Clinical Study Pregnancy Form and reported by the investigator to the sponsor or its designee. Pregnancy follow-up should be recorded on the same form and should include an assessment of the possible relationship to the sponsor's study drug of any pregnancy outcome and follow-up to the first well-baby visit. **Any SAE experienced during pregnancy must be reported on the SAE Report Form and to the sponsor or its designee.**

## 8.6. Definition of an Overdose for This Protocol and Reporting of Overdose to the Sponsor

For this study, an overdose will be defined as  $\geq 1000$  mg (5 times the dose) of MK-3475 or  $> 1000$  mg of epacadostat. No specific information is available on the treatment of overdose of MK-3475 or epacadostat. In the event of overdose, the subject should be observed closely for signs of toxicity. Appropriate supportive treatment should be provided if clinically indicated.

If an AE(s) is associated with ("results from") the overdose of study therapies the AE(s) is reported as an SAE, even if no other seriousness criteria are met.

If a dose of the study therapy (MK-3475) meeting the Protocol definition of overdose is taken without any associated clinical symptoms or abnormal laboratory results, the overdose is reported as a nonserious ECI using the terminology “accidental or intentional overdose without adverse effect.”

All reports of overdose with and without an AE must be reported within 24 hours to the sponsor either by electronic media or paper.

## 8.7. Warnings and Precautions

No evidence available at the time of the approval of this study Protocol indicated that special warnings or precautions were appropriate, other than those noted in the provided IB. Additional safety information collected between IB updates will be communicated in the form of Investigator Notifications (Ins). Any important new safety information should be discussed with the subject during the study as needed. If new, significant risks are identified, they will be added to the ICF.

## 8.8. Data Monitoring Committee

There will be no formal data monitoring committee for this open-label study. For Phase 1, approximately weekly the sponsor will conduct telephone conferences with investigators in order to review cohort-specific data, overall safety data from prior cohorts (if applicable), and to agree on dose escalation, de-escalation, and cohort expansion decisions. For Phase 2, safety and tolerability will be carefully monitored throughout the study by the sponsor in accordance with interim safety analyses planned procedures as described in Section 9.6.

## 8.9. Events of Clinical Interest

Selected nonserious and serious AEs of special interest are also known as ECIs and must be recorded as such in the eCRF and reported to the sponsor within 24 hours either by electronic media or paper. Sponsor contact information can be found in the Investigator Study File Binder (or equivalent). Events of Clinical Interest for this study include:

1. An overdose of sponsor’s product, as defined in Section 8.6 — Definition of an Overdose for This Protocol and Reporting of Overdose to the Sponsor, that is not associated with clinical symptoms or abnormal laboratory results.
2. An elevated AST or ALT laboratory value that is  $\geq 3 \times$  the ULN and an elevated total bilirubin laboratory value that is  $\geq 2 \times$  the ULN and, at the same time, an alkaline phosphatase laboratory value that is  $< 2 \times$  the ULN, as determined by way of Protocol-specified laboratory testing or unscheduled laboratory testing.

**Note:** These criteria are based on available regulatory guidance documents. The purpose of the criteria is to specify a threshold of abnormal hepatic tests that may require an additional evaluation for an underlying etiology. The study site guidance for assessment and follow-up of these criteria can be found in the Investigator Study File Binder (or equivalent).

[REDACTED] This syndrome has been most closely associated with use of MAOIs, meperidine (Demerol®), linezolid, or methylene blue; all of these agents are prohibited during the study. Selective serotonin reuptake inhibitors and SNRIs are permitted in the study. Procedures listed in Section 5.6.5 will be implemented if subjects exhibit the signs and symptoms of SS described in Section 7.5.4, including tremor, hyperreflexia, and spontaneous, ocular, or inducible clonus together with agitation, fever, diaphoresis, or muscle rigidity.

## **8.10. Product Complaints**

The sponsor collects product complaints on study drugs and drug delivery systems used in clinical studies in order to ensure the safety of study participants, monitor quality, and facilitate process and product improvements.

All product complaints associated with material packaged, labeled, and released by the sponsor or its designee will be reported.

The investigator or his/her designee is responsible for reporting a complete description of the product complaint and any associated AEs via email or other written communication to the Incyte contact.

[figure not shown]
If the investigator is asked to return the product for investigation, he/she will return a copy of the product complaint communication with the product.

## 9. STATISTICS

### 9.1. Study Populations

**Efficacy Evaluable:** All subjects enrolled in the study who take at least 1 dose of study drug.

**Safety Evaluable:** All subjects enrolled in the study who take at least 1 dose of study drug.

### 9.2. Selection of Sample Size

#### 9.2.1. Sample Size for the Phase 1 Portion of the Study

The primary objective of the open-label Phase 1 portion of the study is to determine the MTD and DLT of INCB024360 in combination with MK-3475. The total number of subjects will depend on the number of dose levels tested before the MTD is established. Approximately 54 subjects (3-9 subjects per dose level for 4 dose levels plus an additional 9 subjects treated at 50 mg BID, 100 mg BID and potentially at 300 mg BID) will be included based on the dose escalation. Dose escalation will follow a 3 + 3 + 3 design algorithm, as defined in Section 4.1. Based on this algorithm, 3 evaluable subjects are enrolled in each cohort with a maximum of 9 subjects at any dose level (except for MTD or PAD, where a total of 9 subjects will be treated to further evaluate safety and confirm it as the RP2D).

#### 9.2.2. Sample Size for the Phase 2 Expansion Portion of the Study

The sample size of 18 to 42 subjects are expected to be enrolled in each of the 14 response expansion cohorts (NSCLC PD-L1 positive, NSCLC PD-L1 low/negative or indeterminate, melanoma [3 cohorts – checkpoint-naïve, primary refractory and relapsed], transitional cell carcinoma of the GU tract, TNBC, ovarian cancer, SCCHN, DLBCL, MSI high CRC, clear cell RCC, gastric cancer, and HCC). The sample size for each independent cohort yields a power of 80% to detect an increase in ORR by about 20% ( $H_a$ ) from historical response rate ( $H_0$ ). This assumes a 1-sided alpha of 5% and 10% lost to follow-up. See details in Table 21.

A Simon 2-stage design will be used for the primary refractory and relapsed melanoma cohorts. In the first stage for the primary refractory cohort, 8 subjects will be enrolled. If at least 1 response is observed in those 8 subjects, an additional 19 subjects will be enrolled, for a total sample size of 27 subjects. The power for this design is 80% and the Type I error is 3.2%.

In the first stage for the relapsed melanoma cohort, 11 subjects will be enrolled. If at least 2 responses are observed in those 11 subjects, an additional 7 subjects will be enrolled, for a total sample size of 18 subjects. The power for this design is 80% and the Type I error is 2.7%.

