**Statistical Methods:**

Phase 1

Descriptive statistics (eg, mean, standard deviation, range) will be derived where appropriate. Subject enrollment, disposition, demographics, and medical history will be summarized at baseline. The rate of DLTs will be summarized for each cohort. Dose exposure and density will be calculated for each cohort. Safety and disease response data will be compared over time to assess change from baseline, during treatment, and follow-up. [REDACTED]

Phase 2 expansion cohorts

During cohort expansion, approximately 18 to 42 subjects are expected to be enrolled in each of the 14 expansion cohorts (NSCLC [2 cohorts], melanoma [3 cohorts], transitional cell carcinoma of the GU tract, TNBC, ovarian cancer, SCCHN, DLBCL, MSI high CRC, clear cell RCC, gastric cancer, and HCC) and treated at the previously determined RP2D that is not to exceed the MTD. Assuming a 1-sided alpha of 5% and 10% lost to follow-up, the sample size yields a power of 80% to detect an increase in ORR by 20% from historical response rate of each tumor type. The proportion of subjects with ORR by irRECIST v1.1 and Lugano Classification ([Cheson et al 2014](#)) will be tabulated by tumor type (cohort). The PFS and OS will be analyzed by the Kaplan-Meier method. Descriptive statistics (eg, median and range) will be summarized for duration of response and duration of disease control for each tumor type.

[figure not shown]
4.1.2.	Phase 2 Cohort Expansions .....	62
4.2.	Study Endpoints .....	64
4.2.1.	Primary Endpoints .....	64
4.2.2.	Secondary Endpoints – Phase 2 .....	64
	.....	65
4.3.	Measures Taken to Avoid Bias .....	65
4.4.	Number of Subjects .....	66
4.5.	Study Termination .....	66
5.	TREATMENT OF SUBJECTS .....	67
5.1.	Administration of Study Drug .....	67
5.1.1.	INCB024360 .....	67
5.1.2.	MK-3475 .....	68
5.1.2.1.	Timing of Dose Administration of MK-3475 .....	68
5.2.	Treatment Compliance .....	68
5.3.	Randomization and Blinding .....	69
5.4.	Duration of Treatment and Subject Participation .....	69
5.5.	Rationale for Dose Modification .....	69
5.5.1.	Definition of Dose-Limiting Toxicities for Phase 1 .....	69
5.5.2.	Procedures for Cohort Review and Dose Escalation in Phase 1 .....	70
5.5.3.	Procedures for Safety Review for Phase 2 Expansion Cohorts .....	70
5.5.4.	Follow-Up for Dose-Limiting Toxicities .....	70
5.6.	Dose Adjustment of Study Drugs .....	71
5.6.1.	Planned Dose Adjustments .....	71
5.6.2.	Criteria and Procedures for Interruption .....	71

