### 9.4. Statistical Analyses

#### 9.4.1. Primary Analyses

Primary efficacy analysis will be conducted for the Phase 2 efficacy evaluable population. The primary variable for the Phase 2 expansion portion of the study is ORR, which is defined as the proportion of subjects with best response (CR or PR) by irRECIST v1.1 for select solid tumors and modified Lugano Classification (Cheson et al 2014) for DLBCL. The 95% exact CI for the ORR will be estimated using the Clopper-Pearson method. One sample binomial test will be used to test the null hypotheses.

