7.3. Analysis of the Primary Efficacy Parameter

7.3.1. Primary Efficacy Analysis

The primary variable for the Phase 2 expansion portion of the study is ORR, which is defined as the proportion of subjects with best overall response (CR or PR) by irRECIST v1.1 for select solid tumors and modified Lugano Classification (Cheson et al 2014) for DLBCL. Subjects' overall response will be evaluated as CR, PR, SD, PD, or not evaluable (NE) at each postbaseline radiological assessment based on changes in target lesions, nontarget lesions, and appearance of new lesions. The best overall response will be determined from response assessments before and including the date of starting new anticancer therapy. If any alternative cancer therapy is taken while on study, any subsequent assessments will be excluded from the best overall response determination.

For subjects with measurable disease at baseline, the irRECIST version 1.1 assessment criteria presented in Table 5 can be used to determine the overall response at a given timepoint based on the target lesion, nontarget lesion, and new lesion assessment.

Target Lesions	Nontarget Lesions	New Lesions	Overall Response
CR	CR	No	CR
CR	Non-CR / Non-PD	No	PR
CR	NE	No	PR
PR	Non-PD or NE	No	PR
SD	Non-PD or NE	No	SD
Not all evaluated	Non-PD	No	NE
PD	Any	Yes or No	PD
Any	PD	Yes or No	PD
Any	Any	Yes	PD

Table 5: irRECIST for Overall Response: Measurable Disease at Baseline

A subject is considered an objective responder as assessed by irRECIST if they have an overall response of CR or PR at any postbaseline visit. The proportion of responders within each treatment group will be estimated with 90% confidence intervals (CIs) by treatment group. Confidence intervals will be calculated based on the Clopper-Pearson method for binomial distributions. Within each treatment group, 1 sample binomial test will be used to test the null hypothesis.

Using irRECIST criteria, a PD needs to be confirmed as follows.

For each PD, if there is a second PD on the first response assessment that was \geq 4 weeks after the PD, then the PD is defined as confirmed, and the date of progression is the date of the first PD. Otherwise the PD is defined as unconfirmed.

If a subject had an unconfirmed PD, and there are no valid response assessments after that PD (not NE or missing), then the PD will be counted as follows:

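### The 12 one-stage Phase 2 cohorts do not deliver 80% power at a true one-sided 5%: none does after the planned 10% loss, and only three do at full enrolment

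*Protocol*

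**What the plan says.** Protocol 9.2.2 states that "The sample size for each independent cohort yields a power of 80% to detect an increase in ORR by about 20" percent from the historical rate, and adds: "This assumes a 1-sided alpha of 5% and 10% lost to follow-up". SAP 3.4.2 repeats this. The Synopsis drops the word about and says "the sample size yields a power of 80% to detect an increase in ORR by 20% from historical response rate of each tumor type". Protocol Table 21 and SAP Table 4 give a fixed H0, Ha and sample size for each cohort. Protocol 9.3 and SAP 3.3 set the level at one-sided 5%.

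The test is described only as follows: "One sample binomial test will be used to test the null hypotheses" (Protocol 9.4.1) and "Within each treatment group, 1 sample binomial test will be used to test the null hypothesis" (SAP 7.3.1). Neither document says whether it is exact or asymptotic, and neither gives a rejection count for a one-stage cohort.

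The efficacy population in Protocol 9.1 is "All subjects enrolled in the study who take at least 1 dose of study drug"; SAP 5.3.1 agrees. A responder in SAP 7.3.1 is a subject counted as such "if they have an overall response of CR or PR at any postbaseline visit".

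For the two Simon two-stage melanoma cohorts the same section gives error rates to one decimal. For the primary refractory cohort it says: "The power for this design is 80% and the Type I error is 3.2" percent.

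**The concern.** A one-sample binomial test, exact or z, amounts to rejecting when the number of responses reaches a cutoff. With 22 to 42 subjects, moving the cutoff by one response shifts alpha and power by several points. A sample size from a smooth normal formula may therefore have no cutoff that meets both targets.

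Two things are at stake. The first is the accuracy of the stated power. The second is the decision rule: if exact and z cutoffs differ, the same data can be positive under one reading and negative under the other, and the plan does not choose. The Simon figures sit in the same section without a label, so a reader would take both sets of figures to be of the same kind.

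**Working it through.** **1. Reproduce the plan's sample sizes.** Inputs are H0 (p0), Ha (p1) and N from Table 21, one-sided alpha 5%, power 80% and loss 10%. With q = 1 − p:

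n = [(1.645·√(p0q0) + 0.8416·√(p1q1)) / (p1 − p0)]², rounded up; N = n/0.9, rounded up.

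TNBC: (1.645 × 0.3923 + 0.8416 × 0.4877)/0.20 = 5.279; squared, 27.87, so n = 28; 28/0.9 = 31.1, so N = 32, as stated. All 12 cohorts match. In each, n also equals 0.9N rounded down, so n is the plan's own post-loss size.

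**2. True binomial alpha and power.** Take the smallest cutoff r with P(X ≥ r | p0) ≤ 5%. A lower cutoff breaks alpha and a higher one has less power. If power at r is below 80%, no cutoff gives both. Entries are cutoff/size (alpha %; power %). The z-test uses the null variance and no continuity correction.

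| Cohort | H0, Ha | Exact, post-loss n | Exact, full N | z cutoff at full N |
|---|---|---|---|---|
| NSCLC high | 36, 56 | 19/37 (4.0; 77.0) | 21/42 (4.4; 82.6) | same |
| NSCLC low | 12, 32 | 6/22 (4.1; 75.4) | 7/25 (2.4; 73.4) | 6 (7.1; 85.9) |
| Melanoma, naive | 32, 52 | 17/36 (4.0; 77.1) | 19/40 (2.9; 76.7) | 18 (5.8; 85.2) |
| Transitional cell | 24, 44 | 13/32 (2.8; 71.1) | 14/36 (3.4; 78.3) | 13 (7.0; 86.9) |
| TNBC, SCCHN, HCC (each) | 19, 39 | 10/28 (2.8; 70.5) | 11/32 (2.9; 76.1) | 10 (6.8; 86.1) |
| Ovarian | 20, 40 | 10/29 (4.9; 78.5) | 12/33 (2.2; 72.4) | 11 (5.1; 83.1) |
| DLBCL | 36, 57 | 17/33 (4.9; 79.2) | 19/37 (4.0; 80.6) | same |
| RCC | 25, 45 | 13/32 (3.8; 74.9) | 14/36 (4.6; 81.7) | same |
| MSI-high CRC | 57, 80 | 20/26 (2.9; 74.7) | 22/29 (2.9; 79.0) | 21 (6.6; 89.2) |
| Gastric | 14, 34 | 7/24 (4.1; 75.9) | 8/27 (2.8; 74.8) | 7 (7.3; 86.3) |

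Both targets are met in 0 of 12 cohorts at post-loss n and in 3 of 12 at full N.

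**3. Does a z-test rescue the claim at post-loss n?** Seven cohorts keep the exact cutoff and stay at 74.9% to 79.2%. The other five pass 80% only with alpha above 5%: transitional cell 12/32 (6.2; 82.0), TNBC, SCCHN and HCC 9/28 (6.9; 82.5), MSI-high CRC 19/26 (7.0; 86.9).

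**4. Does rounding matter?** The smallest sizes at which any cutoff gives both, in Table 21 order, are 40, 27, 39, 34, 34, 35, 34, 37, 36, 28, 29 and 34. Each is 2 to 6 above the formula n, so rounding 0.9N up leaves the count at 0 of 12. Exact power does not rise steadily with size, which is why checkpoint-naive melanoma passes at 39 but not at its planned 40.

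**5. The Simon cohorts.** Final cutoffs are not printed. With at least 1/8 then at least 3/27, alpha is 3.19% and power 80.02%. With at least 2/11 then at least 5/18, they are 2.71% and 80.05%. Both match the stated figures, so those are true binomial rates and the one-stage figures are not.

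**6. Loss, as an assumption.** All dosed subjects stay in the denominator, so anyone lost before responding counts as a non-responder. The documents do not give the timing of loss. If it lowers the observable response rate to k·Ha, exact power at full N ranges over the cohorts as follows: 72.4% to 82.6% (k = 1), 60.6% to 73.6% (k = 0.95), 41.0% to 63.9% (k = 0.90).

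**The case against.** The strongest points on the other side are these.

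- **The wording says about 20.** Solving for the increase that the exact test detects with 80% power at full N gives roughly 19 to 22 points in the ten cohorts planned at 20. The Protocol 9.2.2 sentence is then nearly true, and the shortfall is at most about 2 points of effect. This fairly describes the size, but it does not cover the fixed Ha values in Table 21 or the Synopsis sentence, which has no such qualifier.
- **0 of 12 uses a denominator the analysis does not use.** This is correct, since dosed subjects are not removed. Full N is the fairer basis for the analysis, and there the count is 3 of 12. The post-loss size still matters because it is where the plan's own calculation places its 80%.
- **The exact interval points to an exact test.** SAP 7.3.1 specifies 90% Clopper-Pearson intervals, whose lower limit exceeds H0 exactly when the exact one-sided 5% test rejects. This is a good reason to name the exact test, but it does not name it. A z-test could contradict that interval: TNBC with 10/32 is rejected by the z-test, yet P(X ≥ 10 | 19%) is 6.8%, so the lower limit falls below 19%.
- **Limited consequence.** Enrolment is closed, the cohorts are proof-of-concept and the report is abbreviated. Some misses are small: MSI-high CRC has 79.0% exact power at full N, and ovarian z-test alpha is 5.1%. This limits the severity but does not make the statement correct.

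**Conclusion.** The concern holds. The 12 sample sizes are correct outputs of a normal approximation, but the 80% power and 5% alpha attached to them are not jointly attained: in no cohort at post-loss n, and only in NSCLC-high, RCC and DLBCL at full N. In the other nine at full N the choice is between an exact test that falls 1.0 to 7.6 points short of 80% power and a z-test that runs 0.1 to 2.3 points over the 5% level. Two of the three that pass, NSCLC-high and DLBCL, are marked in Protocol Table 3 as discontinued before full enrolment, so their full-N figures no longer describe what will be analysed.

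The 0 of 12 and 3 of 12 counts do not depend on which test was intended. They assume that Table 21's H0 and Ha hold and that, at full N, no response is lost to drop-out. The practical issue that remains is the unstated rejection rule, which is worth one response in nine cohorts. It should be corrected. It does not threaten the trial.

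**What to change.** Keep the sample sizes. In Protocol 9.2.2, Table 21 and the Synopsis statistical methods, and in SAP 3.4.2 and Table 4:

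1. Name the test as an exact one-sided 5% binomial test, and say so in Protocol 9.4.1 and SAP 7.3.1 as well.
2. For the 12 one-stage cohorts, replace the single 80% figure with exact power per cohort, stating the size and loss assumption used.
3. List the rejection count and attained alpha at the number analysed. For the one-stage cohorts closed early (NSCLC-high, DLBCL, MSI-high CRC, HCC) use the achieved number.

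Examples at full N with no loss of response: TNBC at least 11/32 (alpha 2.9%, power 76.1%); transitional cell at least 14/36 (3.4%, 78.3%); ovarian at least 12/33 (2.2%, 72.4%); RCC at least 14/36 (4.6%, 81.7%). The Simon power and alpha figures need no change.

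The cost is text and tables, with no added subjects. Naming the exact test holds alpha at 5% and agrees with the SAP's 90% interval, but in nine cohorts it gives up power relative to a z-test: 72.4% to 79.0% instead of 83.1% to 89.2% at full N.

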**Table 3: Phase 2 Cohort Expansions**

Tumor Type	Approximate No. of Subjects Enrolled
NSCLC high positive (PD-L1 TPS $\geq$ 50%) a	42
NSCLC low/negative or indeterminate (PD-L1 TPS 0%-49% or indeterminate) b	25
Melanoma (immune checkpoint-naïve)	40
Transitional cell carcinoma of the GU tract	36
TNBC	32
Ovarian cancer	33
SCCHN	32
DLBCL a	37
RCC	36
MSI high CRC a	29
Gastric cancer	27
HCC a	32
Melanoma (primary refractory) a	27 c
Melanoma (relapsed) a	18 c
Total	446 d

[figure not shown]
a These cohorts were discontinued before full enrollment.

b Subjects whose biopsies are PD-L1 indeterminate will not be excluded from the study, with the exception as noted in inclusion criterion 10a. They will be enrolled under the PD-L1 low/negative group but will be analyzed separately. This may require additional enrollment into the PD-L1 low/negative group to ensure that 25 PD-L1 low/negative subjects are enrolled. Low/negative is defined as TPS of 0% to 49%.

c These 2 cohorts will use a Simon 2-stage design. These numbers represent the maximum total sample size for each cohort. The actual sample size may be smaller.

d Closing of cohorts before full enrollment will result in fewer than 446 subjects.

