#### **7.6.6.1. Tumor Biopsy in the Phase 2 Melanoma Primary Refractory and Relapsed Cohorts**

**Note:** As of Amendment 10, the melanoma primary refractory and relapsed cohorts are closed to further enrollment. The following text applies to subjects enrolled before Amendment 10.

Pretreatment and on-treatment tumor biopsies are required for subjects enrolled in the Phase 2 primary refractory and relapsed melanoma cohorts. Subjects should have tumor lesions that are amenable to repeat percutaneous or endoscopic biopsy. Tumor biopsy samples will be collected at baseline (before Day 1 administration) and while the subject is receiving therapy as specified in the following:

- Screening: A fresh biopsy at baseline is required. Archival samples are not permitted in order to enable analysis of TIL infiltration into tumors during treatment.
- On-treatment biopsy: A biopsy will be collected during Cycle 3 between Days 8 and 15 (Study Days 50 and 57). The biopsy should be collected from the same lesion as the screening biopsy. If the subject progresses before this timepoint, then biopsy should be done at time of progression.

[figure not shown]
[figure not shown]
If a subject is scheduled to have a tumor biopsy for the purposes of this study and it is subsequently determined by the interventional radiologist that tumor tissue cannot safely be obtained, or if the biopsy does not meet the minimum standards for evaluation (as outlined in the Laboratory Manual), then the subject may still enroll in the cohort and will be followed for efficacy and safety. The subject may be replaced in order to enroll sufficient numbers of biopsy-evaluable subjects. Note: If the baseline tumor biopsy was found to be inadequate, the patient should not undergo an on treatment biopsy. Post-progression biopsy can still be optional.

[figure not shown]
Subjects with solitary target lesions should not be enrolled in either of these cohorts.

[figure not shown]
[figure not shown]

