3.4.2. Sample Size for the Phase 2 Expansion Portion of the Study

The sample size of 18 to 42 subjects is expected to be enrolled in each of the 14 response expansion cohorts (ie, NSCLC PD-L1 high, NSCLC PD-L1 low/negative or indeterminate, melanoma, transitional cell carcinoma of the GU tract, TNBC, ovarian cancer, SCCHN, DLBCL, RCC, MSI-high CRC, gastric cancer, HCC). The sample size for each independent cohort yields a power of 80% to detect an increase in ORR by about 20% (Ha) from historical response rate (H0). This assumes a 1-sided alpha of 5% and 10% lost to follow-up. See details in Table 4.

A Simon 2-stage design will be used for the primary refractory and relapsed melanoma cohorts. In the first stage for the primary refractory cohort, 8 subjects will be enrolled. If at least 1 response is observed in those 8 subjects, an additional 19 subjects will be enrolled, for a total sample size of 27 subjects. The power for this design is 80% and the Type I error is 3.2%.

In the first stage for the relapsed melanoma cohort, 11 subjects will be enrolled. If at least 2 responses are observed in those 11 subjects, an additional 7 subjects will be enrolled, for a total sample size of 18 subjects. The power for this design is 80% and the Type I error is 2.7%.

	ORR		
Tumor Type	HO	На	Sample Size
NSCLC high positive (PD-L1 TPS \geq 50%)	36%	56%	42
NSCLC low/negative or indeterminate (PD-L1 TPS < 50% or indeterminate)	12%	32%	25
Melanoma (immune checkpoint-naive)	32%	52%	40
Transitional cell carcinoma of the GU tract	24%	44%	36
TNBC	19%	39%	32
Ovarian cancer	20%	40%	33
SCCHN	19%	39%	32
DLBCL	36%	57%	37
RCC	25%	45%	36
MSI-high CRC	57%	80%	29
Gastric cancer	14%	34%	27
НСС	19%	39%	32
Melanoma (primary refractory)	3%	20%	27 ^a
Melanoma (relapsed)	10%	35%	18 ^a
Total			446

Table 4:Sample Size Calculation for Each Cohort: Comparing With a Known
Proportion

^a Maximum possible sample size for Simon 2-stage design. Actual sample size may be less.

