5.3. Analysis Populations

5.3.1. Efficacy Evaluable Population

The efficacy evaluable population will include all subjects enrolled in the study who take at least 1 dose of study drug. This population will be used for analyses of all efficacy data.

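### The 80% power printed for the two Simon melanoma cohorts is a zero-loss figure, although the sample-size section says every cohort's 80% already allows for 10% lost to follow-up

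*Protocol*

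**What the plan says.** Protocol section 9.2.2 opens by naming all 14 expansion cohorts, including the primary refractory and relapsed melanoma cohorts. It continues: "The sample size for each independent cohort yields a power of 80% to detect an increase in ORR by about 20"%, and then: "This assumes a 1-sided alpha of 5% and 10% lost to follow-up". It refers the reader to Table 21, which lists both melanoma cohorts with H0 and Ha of 3% and 20% (N = 27) and of 10% and 35% (N = 18).

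The two Simon designs follow. For the refractory cohort, "In the first stage for the primary refractory cohort, 8 subjects will be enrolled"; one response or more opens a further 19 places, 27 in all. The design is summarised as "The power for this design is 80% and the Type I error is 3.2"%. For the relapsed cohort, 11 subjects come first; two responses or more open 7 further places, 18 in all. SAP section 3.4.2 repeats both designs and closes the second with "The power for this design is 80% and the Type I error is 2.7"%. Neither document prints the number of responses needed at the end of stage 2.

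Protocol section 9.4.1 tests ORR with a one-sample binomial test, and section 9.3 sets one-sided 5%. SAP section 5.3.1 defines the efficacy population as "all subjects enrolled in the study who take at least 1 dose of study drug". Under SAP section 7.3.1 a CR or PR at any postbaseline visit makes a subject a responder.

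**The concern.** Read in order, section 9.2.2 tells the reader that each cohort's 80% already absorbs 10% loss. If the Simon sizes were set without that allowance, the stated power is not what those two cohorts deliver under the section's own assumption. Efficacy is analysed in all dosed subjects, so a subject lost before any documented response stays in the denominator as a non-responder. The designs are small: one response in 8, or two in 11, decides whether stage 2 opens, so a few lost subjects can matter. SAP Amendment 4 is dated after enrollment stopped, yet it still prints these figures and still plans response tables for both cohorts. A study report could therefore carry the statement forward.

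**Working it through.** **Inputs.** Protocol 9.2.2 and Table 21: refractory n1 = 8, continue if ≥1, n = 27, H0 3%, Ha 20%; relapsed n1 = 11, continue if ≥2, n = 18, H0 10%, Ha 35%; loss 10%.

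**Formula.** With stage-1 minimum a and final cut-off r, the probability of declaring activity at response rate p is the sum over x = a to n1 of P(Bin(n1, p) = x) × P(Bin(n − n1, p) ≥ r − x).

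**1. Final cut-offs.** Solving for the printed Type I errors gives r = 3 and r = 5. Neighbouring values do not fit: r = 2 or 4 gives 10.8% or 0.6% (refractory), and r = 4 or 6 gives 8.7% or 0.6% (relapsed). The one-sample binomial test at 5% leads to the same cut-offs: P(≥3 of 27 at 3%) = 4.6% and P(≥5 of 18 at 10%) = 2.8%.

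**2. Printed figures, no losses.**
- Refractory, p = 0.03: 0.021322 (x = 1) + 0.009223 (x = 2) + 0.001350 (x ≥ 3) = 0.0319.
- Refractory, p = 0.20: 0.3355 × 0.9171 + 0.2936 × 0.9856 + 0.2031 = 0.8002.
- Relapsed, p = 0.10: 0.005474 + 0.010632 + 0.008234 + 0.002751 = 0.0271.
- Relapsed, p = 0.35: 0.06527 (x = 2) + 0.17272 (x = 3) + 0.23086 (x = 4) + 0.33169 (x ≥ 5) = 0.8005.

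All four match the printed values, and the power has almost no slack above 80%.

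**3. Were the other 12 cohorts inflated?** Take n = [1.6449·√(p0·q0) + 0.8416·√(p1·q1)]² / (p1 − p0)², with q = 1 − p, round up, divide by 0.9 and round up again. For NSCLC high positive: (1.6449 × 0.48 + 0.8416 × 0.4964)² / 0.04 = 36.44, then 37, then 37/0.9 = 41.1, then 42.

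| Cohort | n | Rounded up | After ÷0.9 | Table 21 |
|---|---|---|---|---|
| NSCLC high | 36.44 | 37 | 42 | 42 |
| NSCLC low/negative | 21.49 | 22 | 25 | 25 |
| Melanoma, checkpoint-naïve | 35.27 | 36 | 40 | 40 |
| Transitional cell | 31.37 | 32 | 36 | 36 |
| TNBC, SCCHN, HCC | 27.87 | 28 | 32 | 32 |
| Ovarian | 28.64 | 29 | 33 | 33 |
| DLBCL | 32.99 | 33 | 37 | 37 |
| RCC | 31.98 | 32 | 36 | 36 |
| MSI-high CRC | 25.04 | 26 | 29 | 29 |
| Gastric | 23.49 | 24 | 27 | 27 |

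All 12 match. The same allowance on the Simon sizes would give 27/0.9 = 30 and 18/0.9 = 20, not 27 and 18.

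**4. Power with 10% lost, cut-offs held.** Assumption: no lost subject had a documented response.
- Lost subjects kept as non-responders: p = 0.9 × 0.20 = 0.18 and 0.9 × 0.35 = 0.315. Power is 74.6% (refractory) and 70.4% (relapsed).
- Lost subjects removed: 27 × 0.9 = 24.3, taken as 24; 18 × 0.9 = 16.2, taken as 16. Refractory: 77.7% if all losses fall in stage 2 (8 then 24), 74.1% if stage 1 also shrinks (7 then 24). Relapsed: 70.8% (11 then 16) and 70.2% (10 then 16).
- One subject lost in stage 2: 79.4% (8 then 26) and 75.9% (11 then 17).

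**The case against.** The best defence is that the Simon paragraphs stand on their own. They replace the 5% alpha with 3.2% and 2.7%, use increases of 17 and 25 points instead of about 20, and quote power for the particular design. As zero-loss design figures they are correct, and nothing here says they were miscalculated. But the wording about each cohort, the count of 14 and Table 21 all include these two cohorts, and nothing tells the reader that the 10% no longer applies.

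It is also fair to say that the loss figures are near the pessimistic end. A subject lost after a documented CR or PR remains a responder, and a single stage-2 loss in the refractory cohort costs less than one point. That limits the size of the problem, chiefly for the refractory cohort.

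A reader might go further and infer that Type I error is inflated too, because Protocol section 7.6.6.1 says of a subject without an adequate biopsy: "The subject may be replaced in order to enroll sufficient numbers of biopsy-evaluable subjects". The documents do not support that. Replacement is optional. Table 3 says of 27 and 18: "These numbers represent the maximum total sample size for each cohort", and it marks both cohorts as closed before full enrollment. Section 9.2.2 ties the stage-1 decision to the 8 and the 11 subjects. If a cohort did overrun, the one-sample binomial test at 5% would reset the cut-off: to 4 at N = 28, 30 or 33, with single-stage tails of 0.9%, 1.2% and 1.7%, and to 6 at N = 21 or 23, with tails of 1.4% and 2.3%. At N = 20 the relapsed cut-off stays at 5, and the two-stage error with 11 in stage 1 is 4.0%, above the printed 2.7% but inside the 5% level. Keeping treated replacements out of the efficacy analysis would conflict with SAP section 5.3.1.

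**Conclusion.** Wrong as written, and minor. The sentence that gives every cohort 80% power under 10% loss holds as a description of how 12 sizes were built, but not of the two Simon sizes. Under the section's own loss assumption their power is roughly 75% to 78% (refractory) and 70% to 71% (relapsed), and the relapsed cohort carries most of the shortfall. The result rests on two assumptions: the back-solved cut-offs of 3 of 27 and 5 of 18, and no documented response before loss. If some lost subjects had already responded, power lies between these values and 80%. The Type I errors of 3.2% and 2.7% stand for the designs as described. Because both cohorts stopped short of 27 and 18, the correction affects how the design is reported and not how the trial is run.

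**What to change.** In Protocol section 9.2.2 and SAP section 3.4.2, add after the Simon paragraphs that the printed power and Type I errors assume every subject is assessed and contain no allowance for loss. Add that with 10% lost and no response documented before loss, power is about 75% (primary refractory) and 70% (relapsed). Name the final cut-offs on which these figures rest, confirmed by the sponsor as 3 of 27 and 5 of 18 or corrected. Limit the existing 10% sentence to the 12 one-stage cohorts.

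The cost is wording only, with a less favourable stated power for two cohorts. No subjects are added, and the designs, the analysis population and the biopsy-replacement text stay as they are.
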